size based on the observed differences in outcomes such as HRQoL (SF-36 and prostate cancer index, PCI) and cost of PCa care across groups. The primary outcome is HRQoL as measured by the SF-36 and PCI sub-scales. A change of 5 to 9 points on PCI is clinically meaningful [272]. Similarly, a difference of 7 points or more on the SF subscales is considered clinically meaningful [272, 275, 301]. Based on our prior research and that of Litwin et al [253, 272], the standard deviations for the PCI and SF-36 scales in samples of men with PCa mostly range from 8 to 14; hence standardized differences (SDs) of $7/14=0.5$ to $7/8=0.87$ will be clinically relevant. The power calculations for Aims 2-4 assume availability of 720 participants who are eligible for randomization into one of the two intervention groups. We assume a conservative intra-class correlation of 0.3 and 4 follow-up measures per subject. The sample size is adjusted to accommodate a 10% missing or dropout rate by 24 months based on rates over a similar period of time in previous studies [272, 275, 301]. We assume 80% power and two-sided level of significance of $\alpha = 0.05$. We have 80% power to detect a 1.2 point difference in PCI or SF-36 sub-scale. Within treatment type, the sample size is reduced to 60 per intervention arm. We have 80% power to detect a 3.0 point difference in sub-scale with 60 patients in each arm. Thus, we will have adequate power to detect differences between treatment groups [302]. Power for identifying utility based profiles and outcomes: We analyzed the levels of power for differences in outcomes between profiles defined by latent classes of attributes-specific utilities with a conservative allocation of subjects to each profile (25 in one vs. 10 in other profile) and less conservative allocation (35 in one profile vs. 35 in other profile) using a logistic model based comparison for a binary outcome (e.g. recovery of baseline HRQoL) with a 2-sided alpha of .0125 (Holms adjustment profiles). In the first allocation, the group difference of 0.56 yields 80% power; for the second allocation an effect size of 0.42 corresponds to power of 90. Thus, with our anticipated effect size of 0.51, we will have adequate power with $n=60$ in each group. (Adjusting for patient characteristics may reduce the effect sizes of the differences between profiles.)

Key inclusion criteria

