
The following documents are currently attached to this item:

There are no documents attached for this item.

Analysis Plan

Analytic Methods General: The statistical analysis will proceed in three stages: First, we will check the data quality and carry out descriptive analyses of demographics and key outcome variables. Next, we will assess preferences using conjoint analysis and inferential analysis. For continuous outcome variables, we will check for homogeneity of errors using spread-vs.-level plots and will consider transforming variables that either are highly skewed or have variance that depends strongly on the mean. We will use methods based on general linear model (univariate and repeated-measures ANOVA, mixed models) to analyze uncensored continuous outcomes, such as generic and prostate-specific HRQoL, psychological wellbeing and satisfaction with care. For potentially censored outcome variables such as time to PSA recurrence, we will use Kaplan-Meier curves and Cox proportional hazard models. Poisson regression (zero-inflated) will be used for count data. We will use Bonferroni correction for multiple testing. We will use propensity-score and instrumental variable approach to minimize observed and unobserved bias within groups (i.e. intervention group and usual care control group). **Missing Data:** We will attempt to prevent missing data by ensuring that data collection is as complete as possible. Should there be substantial missing data, however, we will employ analysis and imputation methods to reduce bias and increase efficiency [279-282]. Based on the proportion of missing data, we will use complete-case analysis, or explore available techniques, such as standardized score imputation, simple means imputation, maximum likelihood model-based imputation, data augmentation, etc. [281]. When data are evidently non-missing at random, we will conduct explicit non-ignorable modeling and sensitivity analysis [278]. **Propensity score matching:** In observational studies, comparisons between treatment groups that do not adjust for factors associated with treatment choice may be biased. Propensity score technique offers a highly practical approach to address such bias [283]. Here, the probability of each participant being in the treatment arm (i.e., the propensity score), is estimated. Participants are sorted by their propensity scores; the sample is divided into strata based on estimated scores, the treatment effect within each stratum estimated and overall estimate computed by aggregating across strata in a weighted analysis. When the model for predicting treatment status includes all relevant covariates, within strata treatment groups will be balanced on all predictors and the overall comparison of treatment arms will have substantially lower bias. We will use a model relating PCa treatment (RP, RALP, EBRT, PT, BT or AS) to baseline factors [283-284]. To study the extent to which treatment groups are now matched, we will compare t-statistics for these covariates before and after adjusting for propensity score. This will be done separately for intervention group and usual care controls. **Instrumental variable analysis:** Another limitation of observational research is the strong potential for confounding bias, due to differences in comparison groups that are not reflected in the data (i.e., unobserved bias). The instrumental variable (IV) approach is useful in reducing this bias. This technique uses one or more observable factors that influence outcome only indirectly (the IV). This allows one to mimic randomization with different likelihoods of receiving a particular treatment [227, 285-291]. Physicians play an important role in patients treatment choice- a majority of the PCa patients report that their physicians recommendation was the most important factor in their treatment choice [11-12, 37-46, 51, 55-56, 60-64]. We will use specialty of the first physician (urologist, urologic oncologist, oncologist, radiation oncologist) who the patient saw during PCa diagnosis as an IV. We will explore other potential IVs, such as absolute distance between patients residence to the hospital where they will receive care (Hospital of University of Pennsylvania, Presbyterian Medical Center, PVAMC, Pennsylvania Hospital, or Fox-Chase Cancer Center). Validity of the IV(s) is assessed as following. First, we will use Pearsons correlation coefficient to examine the correlation between IV, primary exposure (treatment) and outcomes. We will then perform a partial F-test using a linear regression where treatment group is regressed on physician specialty along with patient attributes. For a valid IV, test statistic should be very high (e.g., physician specialty will strongly predict treatment after adjusting for covariates). Next, we will perform a partial F-test using a linear probability model in which HRQoL outcomes are regressed on specialty and patient demographic and clinical variables. For an IV to be valid, this test statistic should be very low. Finally, we will compare observable attributes across patient groups cared for by different physician specialty (initial). For the IV be valid, these groups should have comparable observable attributes. **Phase 1 Focus group analysis-development of conjoint task instrument:** The goal of focus groups is to identify attributes of PCa treatment that are most salient to localized PCa patients. This process includes following steps: (1) identifying and defining attributes; (2) assigning attribute levels; and (3) creating scenarios and choice sets. Attributes will be defined based on input from patient focus groups, literature, our prior research, and prior physician focus group. Once an attribute and its extreme values are defined, we will assign them appropriate levels. A large number of possible combinations of attributes and levels will preclude

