patients in decision (measured using CPS) using multi-nominal regression model to adjust for observed covariates. Then we will examine if these associations vary across intervention and usual care control groups. We then will repeat the model with other independent variables (decision conflict and trust). Next, we will test the association denoted by path c (direct effect of DCS, CPS, and trust on outcomes). For continuous outcomes (HRQoL, AUA-SI, MAX-PC, CES-D, SWD, and PSQ-18), we will compute area under the curve (AUC) for each measure for each patient. We will analyze AUC summaries with univariate linear models. In our main analysis we will analyze the series of functional status measures using linear mixed models that predict the outcome from time, independent variables and their interaction. We will repeat the analyses described for path c, this time by including treatment received in the models. We will test if the observed effects of DCS, CPS or trust on outcomes will be weaker after controlling for treatment. These analyses will be performed within and between groups (intervention and usual care controls). Specific Aim 3: Hypothesis: Prostate cancer patients in the intervention group undergoing conjoint analysis-value clarification exhibit improved treatment choice, satisfaction with decision, lower regrets, and improved objective and subjective outcomes. Analysis for Specific Aim 3 uses intent-to-treat approach: all randomized participants will be included regardless of whether they drop out of the intervention or study. Analysis will involve comparison of the primary outcomes between intervention and usual care control groups. Improved treatment choice is operationalized as the likelihood of low-risk PCa patients receiving active surveillance than active treatment, and will be compared between intervention and usual care control group. To allow for different trajectories of the outcome measures and to afford flexibility in making contrasts within participants over time and across participants, while simultaneously controlling for potential confounders, we propose the participant-specific or mixed effects linear model, in which the mean outcome depends on fixed covariates and random effects. The primary fixed effects will be indicators for intervention group and hospital. We will also stratify the analysis by type of treatment. The random effects represent the unobserved factors that lead to variation of the individual participants outcome. Random intercepts for each participant permit modeling of natural variation across participants at baseline. In addition, random slopes or random effects for the trajectory of each participant over time, allow for variation of each participant about a mean, overall trajectory across all participants. Although less robust to model misspecification, the mixed effects paradigm offers special flexibility in longitudinal data when exposures vary over time and when dropout and missed visits lead to unbalanced groups. The target of inference is the participant-specific response to treatment over time. At each time point of interest, we will estimate from the fitted model the difference from baseline in outcome for the treatment and control groups and test the difference between these differences. Both univariate and multivariate results will be reported in terms of Wald test, point estimates, and 95% confidence intervals. Specific Aim 4: Hypothesis 4: Prostate cancer patients whose treatment is more concordant with their values markers will experience improved subjective and objective outcomes. This specific aim s for intervention group only. We will analyze the association of the concordance between stated individual preferences and actual treatment received with objective (PCa recurrence and complications), subjective (HRQoL, psychological wellbeing, SWD, and satisfaction with care) outcomes, across treatment groups, adjusting for covariates. Association between the value markers (profiles) and measures of outcomes and personal and clinical characteristics: The value markers will be studied for their relationship with socio-demographic and clinical characteristics. We will also assess the association of value markers with outcomes. We will perform logistic regression with outcomes as the dependent variable and dummy variables for the utility-based profiles obtained earlier as independent variables. We will perform this evaluation with and without adjusting for patient attributes in the logistic model. For each case (adjusting and not adjusting for patient attributes), the evaluation of association between these profiles and outcomes will be based on a likelihood ratio test of the set of odds ratios corresponding to the dummy variables of the profiles. Additionally, we will perform a sequence of pair wise tests of comparisons of the profiles in terms of the proportion of type of treatment received based on the Holms multiple comparisons approach. This procedure is hierarchical in that it will identify the utility-based profile at the start of the process before making other comparisons, thus protecting the Type I error from additional comparisons. Specifically, Holms approach tests each pair-wise comparison in ascending order of p-values. Successively larger p-values have less rigorous alpha. The sequential Holm tests terminate after the first non-significant comparison so no subsequent comparison is significance. Concordance and its assessment: Understanding and respect for the patients preference and values is the main aspect of concordance [69, 73]. Thus a first step in concordance involves the physician extracting and understanding the patients view, followed by an agreement between the physician and patient regarding a management plan that integrates their views. There exist many definitions of concordance. For the purpose of this study, we operationalized concordance as agreement between a patients value markers and the attributes (or characteristics) of the treatment that

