
the patient receives (choice). Association of concordance between stated preference and attributes of treatment received will be studied separately for each treatment using Kappa statistics. The degree of concordance then will be used as an independent variable to test its association with outcomes. For objective/clinical outcomes (i.e., complications and PCa recurrence), we will test the hypothesis that degree of concordance is associated with PCa recurrence (measured by PSA doubling time). To evaluate the effects of concordance on biochemical recurrence of PCa, we will analyze PSA levels on the log scale over time using a mixed model approach. We also will apply survival analyses (Kaplan-Meier, logrank and Cox model) to model effects concordance of treatment and covariates on time to PSA recurrence. For subjective outcomes of urologic symptoms (AUA-SI), generic and prostate specific HRQoL, psychological well-being (CES-D, MAX-PC), satisfaction with decision and satisfaction with care, we will perform inferential analysis with t, chi-squared and non-parametric tests. Wilcoxon matched-pairs test will be used for comparisons within concordance and non-concordance groups. A concordance group will be defined as at least 75% agreement between values markers and treatment related attributes. We will perform sensitivity analysis to test robustness of results. Primary analyses will compare baseline with six and 24 months assessments, as literature suggests these are the clinically most relevant time points. Secondary analyses will compare baseline with three month and one year outcomes. Proportion returning to baseline over time will be compared using chi-squared tests, using procedures such as Bonferroni, Scheffé, and step-down Holm corrections to adjust for multiple testing. We will use loglinear regression models with psychological well being, HRQoL and satisfaction with care scores (log) as dependent variables, logistic regression with return to baseline as the dependent variable, and degree of concordance as the independent variable. For repeated measures outcomes we will use linear mixed models (Proc Mixed).

The following documents are currently attached to this item:

There are no documents attached for this item.

Deception

Does your project use deception?

No

Data confidentiality

- x Paper-based records will be kept in a secure location and only be accessible to personnel involved in the study.**

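### The general multiplicity rule is single-step Bonferroni, where step-down Holm, already used elsewhere in the plan, gives the same error bound with more power; the Aim 4 list of procedures should be closed

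*Combined protocol and SAP*

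**What the plan says.** The combined protocol and SAP treats multiplicity in four places.

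- Analysis Plan, Analytic Methods General: "We will use Bonferroni correction for multiple testing". No family and no number of tests are given.
- Analysis Plan, Specific Aim 3 (the randomised comparison): the primary outcomes are compared between arms with mixed models, Wald tests and 95% confidence intervals at each time point of interest. No multiplicity method is named, so the general rule applies.
- Analysis Plan, Specific Aim 4, profile comparisons: pairwise tests are "based on the Holms multiple comparisons approach". The procedure is described correctly: "Holms approach tests each pair-wise comparison in ascending order of p-values. Successively larger p-values have less rigorous alpha". The power text under Accrual matches this, "with a 2-sided alpha of .0125 (Holms adjustment profiles".
- Analysis Plan, Specific Aim 4, proportion returning to baseline: chi-squared tests "using procedures such as Bonferroni, Scheffé, and step-down Holm corrections to adjust for multiple testing".

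Two sections differ on what is primary. Primary outcome variable(s) lists six constructs: recurrence, complications, HRQoL, psychological well-being, satisfaction with decision and satisfaction with care. No secondary outcomes are listed. The power text under Accrual instead names HRQoL on the SF-36 and PCI sub-scales as the primary outcome.

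**The concern.** There are two separate points.

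First, the general rule is the less powerful of two procedures that share the same error guarantee, and the plan already uses the better one for its profile comparisons. Power for Aims 2-4 was planned at an unadjusted two-sided 0.05, so any correction reduces the stated 80%. It makes sense not to give up more than the error bound requires.

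Second, for return to baseline the plan offers an open list. The correction that is finally applied could be chosen after the results are known. One listed option, Scheffé, was developed for contrasts of means in a linear model, and the plan describes no adaptation of it to chi-squared comparisons of proportions.

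**Working it through.** **The plan's own figures.** The profile alpha is 0.05/4 = 0.0125, which is the first Holm step for four tests (0.0125, 0.0167, 0.025, 0.05).

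The detectable differences under Accrual come from (z0.975 + z0.80) × SD × √[(1 + 3 × 0.3)/4] × √(2/n). Here z0.975 + z0.80 = 2.80, the intra-class correlation is 0.3, there are four measures, and n is reduced by 10% for dropout.
- n = 324 per arm, SD 8: 2.80 × 8 × 0.689 × 0.0786 = 1.21 points (plan: 1.2).
- n = 54 per arm, SD 8: 2.80 × 8 × 0.689 × 0.192 = 2.97 points (plan: 3.0).

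Both reproduce at the low end of the stated SD range (8 to 14) and at unadjusted alpha 0.05.

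**Why Holm dominates Bonferroni.** With m tests, Bonferroni compares every p-value with 0.05/m. Holm compares the i-th smallest with 0.05/(m − i + 1) and stops at the first failure. No Holm threshold is below 0.05/m, so every Bonferroni rejection is also a Holm rejection. If m0 null hypotheses are true, the first of them to be rejected faces a threshold of at most 0.05/m0. The chance of any false rejection is therefore at most m0 × 0.05/m0 = 0.05, whatever the dependence.

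**Size of the gain.** The plan gives no family size, so m is an assumption and a range is shown. Each real effect is given 80% unadjusted power (mean z of 2.80). Bonferroni power per real effect is then Φ(2.80 − z), where z is the two-sided critical value at 0.05/m. For m = 6, Φ(2.802 − 2.638) = 0.565. Holm was simulated with 200,000 replicates per scenario, using correlations 0 and 0.5 for m = 4, 8 and 12, and 0, 0.3 and 0.6 for m = 6.

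| m | 0.05/m | Bonferroni | Holm, half real | Holm, all real |
|---|---|---|---|---|
| 4 | 0.0125 | 0.62 | 0.64-0.65 | 0.71-0.73 |
| 6 | 0.0083 | 0.57 | 0.59-0.60 | 0.66-0.68 |
| 8 | 0.00625 | 0.53 | 0.56 | 0.64 |
| 12 | 0.0042 | 0.47-0.48 | 0.51 | 0.58 |

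- Under the global null, family-wise error is identical for the two methods (0.037-0.049).
- With half the nulls true, it is 0.021-0.025 for Bonferroni and 0.030-0.039 for Holm.
- The chance of at least one rejection is the same for both.
- No replicate had a Bonferroni rejection that Holm missed.

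**The Aim 4 list.** Choosing between Bonferroni and Holm after the fact amounts to Holm, because Holm's rejections contain Bonferroni's. For all pairwise comparisons among g groups, the large-sample Scheffé critical value √χ²(0.95; g − 1) exceeds Bonferroni's: 2.45 against 2.39 for g = 3, and 3.33 against 2.94 for g = 6. Scheffé is therefore stricter there. With four or more contrasts among three groups the order reverses: Scheffé stays at 2.45, while the first Holm step for four tests needs 2.50.

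**The case against.** The strongest reply is that nothing here is an error. Bonferroni is valid under any dependence, gives matching simultaneous intervals, and lets each outcome be judged without reference to the others. That stands.

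The reply on size also has force. The text under Accrual treats 7 points on an SF-36 sub-scale as clinically meaningful. Take SD 14, 324 per arm and a single time point: 7/(14 × √(2/324)) = 6.36, so Bonferroni power exceeds 0.999 for 6 or 12 tests. For 5 points the ratio is 4.55 and power is 0.97 or 0.95. For the main HRQoL comparison, then, a meaningful difference would be found under either method. Efficiency matters for small differences and for the analyses within treatment type. With 54 per arm, 7/(14 × √(2/54)) = 2.60, and power falls from 0.74 unadjusted to 0.48 under Bonferroni with six tests. It may also matter for primary outcomes with no power calculation, such as recurrence and satisfaction.

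A reader might infer more than the documents support:

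- *Bonferroni is fixed for the whole trial.* It is the general rule, but the Aim 4 profile comparisons and their power calculation use Holm.
- *There are six tests, each at 0.0083.* Six is the number of constructs under Primary outcome variable(s). The power text points to sub-scales, the SF-36 alone has eight domains, and Aim 3 tests at several time points.
- *The gain is dramatic.* For six tests at correlation 0.3, the chance of confirming all six does rise from 12% to 36%, but only if all six effects are real and each has 80% unadjusted power. With two real effects, average power moves from 57% to 58%; with one, there is no material change.
- *The open list destroys error control.* Between Bonferroni and Holm it does not. Error can leak only through Scheffé in some settings, or through an unnamed procedure, because the list is illustrative. The list also applies to an analysis confined to the intervention group.

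**Conclusion.** The point holds as a loss of efficiency together with an unfinished specification. Type I error is not inflated by the general rule. Holm's superiority to Bonferroni in rejections is exact and needs no added assumption. Its size depends on a family that the plan does not define: for 4 to 12 tests at 80% unadjusted power, about 2-3 points of average power per true effect if half are real and 9-12 points if all are. The claim of never having less power applies against Bonferroni only, since Scheffé can be less strict than Holm's first step in some settings. The Aim 4 list needs one named procedure because Scheffé does not fit the tests it is attached to and the list is open-ended. This is a worthwhile improvement at little cost; it does not threaten the trial's validity.

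**What to change.** 1. In Analytic Methods General, replace Bonferroni with step-down Holm at two-sided 0.05, applied to a listed family of primary tests.
2. List that family by outcome, scale and time point. The list must reconcile the six constructs under Primary outcome variable(s) with the SF-36 and PCI sub-scales named under Accrual. Without it, two analysts could build different Holm families from the same plan.
3. In Specific Aim 4, for the proportion returning to baseline, name Holm alone and delete Scheffé and the open-ended wording.

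The two method changes are matters of wording; the family list needs a decision by the investigators. No additional patients or data are needed. The one real cost is that Holm has no simple matching simultaneous confidence intervals. The plan reports 95% intervals and mentions no simultaneous ones, so nothing explicitly planned is lost, but it should say that the intervals are unadjusted if that is intended.
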